1.3 RATIONALE

SCLC is a common disease, with a high propensity for brain metastases. Although the use of PCI has for a long time been considered a standard therapy for patients with both LS-SCLC and ES-SCLC, recent results from a randomized trial examining PCI vs observation with frequent use of brain MRI imaging, revealed no difference in outcomes.¹⁸ The findings of this study have changed the practice in large academic institutions overnight (*personal communication*), and patients with ES-SCLC are no longer offered PCI as a standard of care in many academic centers in the United States. Large cooperative groups are planning to start a similar randomized trial for patients with LS-SCLC. Overall, this leaves patients with very limited treatment options, and given the high risk of brain metastases, the need for novel therapies is greatly needed.

TTFields therapy has entered the oncology treatment landscape as an FDA-approved cancer treatment for recurrent GBM and is part of the National Comprehensive Cancer Network (NCCN) Treatment Guidelines for this disease. The success of this approach in reducing the risk of recurrent GBM has been adopted in the randomized phase 3 METIS trial for patients with known brain metastases from NSCLC, which is currently on-going at many US centers. We hypothesize that TTFields can be similarly adapted to prevent the formation of SCLC metastatic brain lesions. TTFields therapy is shown to be safe and lacks the conventional cytotoxic systemic side effects. Thus this alternative interventional could significantly decrease the brain metastatic rate as well as lower the need for toxic whole brain irradiation

This study will evaluate the potential for TTFields therapy as a novel approach to reducing the rate of in-brain failures in patients with SCLC that have completed standard-of-care chemo-radiotherapy. It is hypothesized that TTFields therapy can be used prophylactically to reduce the incidence of brain metastases as compared to historical observational reports, and have no effect on the cognitive function of those receiving this treatment modality.

1.4 POTENTIAL RISKS AND BENEFITS

KNOWN POTENTIAL RISKS

Refer to Section 9.4.1 for a detailed description of any adverse events that have been recorded in patients with GBM on clinical trials investigating TTFields therapy, after brain-directed therapies (such as surgery, radiation therapy), systemic therapies, and most often with evidence of GBM progression.

Results from a randomized study examining TTFields therapy in patients with newly diagnosed GBM showed that the only TTFields-related AEs are skin irritation, falls that were observed at a slightly higher incidence among patients carrying the Optune® device, headaches related to wearing the transducer arrays 24 hours a day, and mild psychiatric symptoms (e.g., anxiety, insomnia, confusion) that could be caused by the need to incorporate the device and arrays into daily life.

Since TTFields are only applied to the brain, they are unlikely to have an effect on rapidly proliferating cells in the rest of the body.

KNOWN POTENTIAL BENEFITS

Given the high rate of brain metastases among patients with SCLC, prophylactic TTFields therapy may reduce the risk of brain metastatic lesions and improve overall patient outcomes. It cannot, however, be guaranteed that participants in this study will directly benefit from treatment during participation, as the clinical trial is designed to provide information about the safety and effectiveness of this investigational approach.

2. OBJECTIVES

2.1 PRIMARY OBJECTIVES

Observed rate of brain metastases following TTFields therapy at 6 months

2.2 SECONDARY OBJECTIVES

1. Observed rate of brain metastases following TTFields therapy at 12 months.
2. Survival of participants with SCLC after using TTFields therapy.
3. Usage and overall safety characteristics of TTFields therapy.
4. Quality of life among participants using TTFields therapy.
5. Observed rate of SCLC brain metastases at 6 month from the beginning of the 4th cycle of chemotherapy to development of brain metastases

3. STUDY DESIGN AND ENDPOINTS

3.1 DESCRIPTION OF THE STUDY DESIGN

Refer to Section 10, STATISTICAL CONSIDERATIONS for additional information regarding statistical methods used in this study.

This is a Phase II pilot study to assess the safety and efficacy of prophylactic TTFields therapy in patient with SCLC. Participants must meet the inclusion criteria, have none of the exclusion criteria, and have provided written informed consent before the conduct of any screening tests not performed routinely in their treatment.

Participants with either LS-SCLC or ES-SCLC must be no more than 6 weeks from having received last dose of chemotherapy for primary tumor (per institutional guidelines), and must have at least demonstrated a partial response to treatment, to be considered eligible for TTField therapy with the Optune® device. Participants are encouraged to undergo TTField therapy (200 kHz) for a minimum of 18 hours per day for a period of 12 months, or until the confirmed appearance of metastatic brain lesions, whichever comes first. Participants that develop numerous (>10) supratentorial metastatic lesions before 12 months will discontinue further use of TTFields and will receive palliative/supportive care per institutional guidelines (e.g., whole brain radiotherapy). Participants that develop either limited (≤ 10) supratentorial or any number of infratentorial metastases will remain eligible to continue with TTFields therapy for the duration of the 12 months after the brain metastatic lesions are addressed according to institutional guidelines (e.g. partial brain irradiation stereotactic radiosurgery, stereotactic body radiation therapy). Systemic progression will be managed per institutional guidelines (e.g. systemic chemotherapy, immunotherapy, radiation therapy, etc.) and patients will remain eligible to continue with TTFields therapy for the duration of the 12 months. While on-study, participants will be clinically evaluated every 2-3 months per NCCN guidelines and will all be monitored remotely by phone calls monthly and will undergo gadolinium (gd)-MRI of the head at 6 months to assess occurrence of disease progression (per RECIST v1.1). Participants will be subject to periodically answering quality of life (QoL) questionnaires (i.e., baseline, 6 and 12 months after initiating treatment). At the end of study, participants will undergo clinical follow-up 1 and 3 months after completion of TTField therapy. Subsequent follow-up until death (up to 5 years) will be in accordance with standard of care (i.e., every 3 months during years 1 and 2 following last chemo-radiotherapy, then every 6 months thereafter).

3.2 STUDY ENDPOINTS

PRIMARY ENDPOINT

Objective	Endpoint	Start	End
Observed rate of brain metastases following TTFields therapy at 6 months	Incidence of SCLC brain metastases at 6 mo	Start of TTFields [baseline]	6 mo

SECONDARY ENDPOINTS

Objective	Endpoint	Start	End

Observed rate of brain metastases following TTFields therapy at 12 months	Incidence of any SCLC brain metastases at 12 mo	Start of TTFields [baseline]	12 mo
Overall survival of participants with SCLC after using TTFields therapy.	Overall survival	Start of TTFields [baseline]	Death or last follow-up at 60 months.
TTFields therapy related side effects.	1. Incidence of TTFields related AEs 2. Incidence of cognitive AEs using Mini Mental State Exam (MMSE)	Start of TTFields [baseline]	12 mo 6, 12 mo 12 mo
Quality of life among participants using TTFields therapy.	EORTC QLQ-C30 questionnaire at 6 and 12 mo	Start of TTFields [baseline]	6, 12 mo
Observed rate of SCLC brain metastases at 6 month from the beginning of the 4 th cycle of chemotherapy to development of brain metastases	Incidence of SCLC brain metastases at 6 month from the beginning of the 4 th cycle of chemotherapy to development of brain metastases	Start of the 4 th cycle of chemotherapy [baseline]	6 mo

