6. TREATMENT PLAN

6.1 DOSAGE AND ADMINISTRATION

In this study, a treatment cycle is defined as 4 weeks (or 1 month). Using the Optune® device, participants will receive multiple 1-month treatment courses, in which TTField therapy will be administered to the participants' head continuously (18-24 hours per day) for the entire duration of the 12 month study, or until disease progression, whichever comes first.

Treatment will be administered on an out-patient basis. Reported adverse events and potential risks are described in Section 9. No investigational or commercial agents or therapies other than those described in this protocol may be administered with the intent to treat the participant's malignancy.

ELECTRIC FIELD

Participants receiving TTField therapy will have 4 transducer arrays placed on their scalp and connected to the portable Optune® device which will be set to generate 200 kHz electric field in 2 perpendicular directions that are operated sequentially. The field intensity will be set at >0.7 V/cm at the center of the brain. These device settings are preset by the manufacturer. Participants will receive detailed written instructions and practical training by the Principle Investigator or designated member of the study team on how to operate the device for continuous at-home treatment.

TRANSDUCER ARRAY PLACEMENT

TTFields are applied to the shaved scalp via two pairs of orthogonally positioned transducer arrays. Since no brain metastatic lesions are present (or clinically observable) at time of enrollment, there is no need to precisely position arrays around a tumor as is the case in treating GBM.^{20,21} Instead to create the 2 perpendicular field directions, each pair of transducer arrays will be centered on the participants head such that one pair is placed on the left and right side of the head, and the second pair placed anteriorly and posteriorly. Transducer arrays should be replaced every 2 to 3 days, with a slight relocation of the new arrays ~2 cm from prior location (**Figure 4**).

[figure not shown]

Figure 4: Transducer array layouts found to deliver a uniform field distribution to the entire brain. Each layout comprises two pairs of arrays. One layout comprises the pairs of arrays shown in schematics A and B. The second layout comprises the pairs of arrays shown in schematics C and D.

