A gd-MRI of the head is required within 12 weeks prior to enrollment to assess presence of metastatic brain lesions. On-study, Gd-MRI will occur per standard of care, with imaging taking place every 3 months for the first 24 months, after which participants will have Gd-MRI every 6 months.¹⁸ The brain MRI protocol specifies 1.5 Tesla magnetic resonance imaging and includes axial images of 3 mm slice thickness with T1-post gadolinium, T2 and T2 flair sequences. All MRI images will be centrally reviewed by expert neuroradiologist at OHSU.

All subsequent imaging assessment should be performed according to Schedule of Events (Section 7.8).

PATIENT REPORTED OUTCOMES

QoL care metrics will be assessed according to Schedule of Events (Section 7.8). Study participants will be asked to complete 2 questionnaires, each of which will be conducted prior to

TTField therapy (i.e., baseline), and again at 6 and 12 from starting TTField therapy (Table 3). The purpose of completing the questionnaires is to obtain a rich description of patients' experiences of QoL and various symptoms. It will take <45 minutes to complete the questionnaires. The validated questionnaires were selected based on our clinical knowledge and experience with this patient population.

Table 3. Method and Timing of QoL Assessments				
	Measurement	Baseline	6 months	12 months (i.e. EOT)
QoL	EORTC QLQ-C30	X	X	X
MMSE	Mini Mental State Exam	X	X	X

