7.4 ASSESSMENTS DURING TREATMENT

Refer to the schedule of events (Section 7.8) for timing and details of specific procedures to be conducted. Except for head MRI scans that is scheduled every three months for the 1st year while participants are on-treatment, all other imaging will be in accordance with standard-of-care guidelines. Clinical evaluations are scheduled to occur every two months for ES-SCLC patients, and every three months for LS-SCLC patients while participants are on-treatment. Follow-up phone calls will occur every other month for months patients are not seen for clinical evaluation at the clinic. Follow-up and clinical evaluations will resume to standard-of-care after completion of the treatment period. Imaging can be done within \pm 1 week. All other studies can be obtained \pm 3 days of the stated time point.

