7.5 END OF TREATMENT VISIT

The end of treatment (EOT) visit should be conducted 10 \pm 10 days following completion of TTField therapy. All AEs that occur prior to the EOT visit should be recorded. Participants with an AE of Grade > 1 will be followed until the resolution of the AE to Grade 0-1 or until the beginning of a new anti-cancer therapy, whichever occurs first. Imaging (CT and/or MRI as appropriate) will be used to assess disease staging.

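### The schedule of events has no head MRI between week 36 and the 3-month follow-up visit, so if sites follow it the 12-month brain-metastasis incidence is not measured at 12 months

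*Combined protocol and SAP*

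**What the plan says.** The secondary endpoint in Section 3.2 is "Incidence of any SCLC brain metastases at 12 mo", counted from the start of TTFields. Section 10.2 gives it the analysis of the primary endpoint: an incidence with a 95% confidence interval, and a one-sample test in each disease group.

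Head imaging around month 12 is described in four places:

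- Section 7.1, imaging subsection: "On-study, Gd-MRI will occur per standard of care, with imaging taking place every 3 months for the first 24 months". The same subsection then refers later imaging to the schedule in Section 7.8.
- Section 7.4: "Except for head MRI scans that is scheduled every three months for the 1st year while participants are on-treatment".
- Section 7.5, on the end-of-treatment visit: "Imaging (CT and/or MRI as appropriate) will be used to assess disease staging". This allows a brain MRI but does not require one.
- Section 7.8, Gd-MRI row: marks at screening, weeks 12, 24 and 36, and the 3-month follow-up visit. Weeks 40, 44 and 48 and the 1-month visit are blank.

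Three further provisions matter. Section 6.1 says that "a treatment cycle is defined as 4 weeks (or 1 month"), which puts month 12 at week 48, the last treatment column of the table. Section 8.3 dates a lesion that was equivocal and later confirmed to the scan on which it was first seen. Section 10.4 allows other time points to stand in where a time point has no data, and rules out imputation.

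**The concern.** The text implies a head MRI at month 12 and the table does not contain one. No rule says which governs, and because Section 7.1 hands later imaging back to the table, a site could reasonably follow the table alone.

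Brain metastases without symptoms are found only by scanning. With no scan at the landmark, the status at month 12 of a participant who was clear at week 36 is unknown unless symptoms lead to an unscheduled scan. The reported 12-month incidence would then depend on how the analyst treats a lesion first seen at the follow-up scan, and the plan leaves that choice open until the data are in hand.

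**Working it through.** **Reading the table.** The Gd-MRI row has 15 positions: screening, twelve 4-weekly columns, and two follow-up columns. Counted against the header, the marks fall at screening, 12, 24, 36 and +3 months. The hematology and biochemistry rows do carry a mark at week 48, so the blank is specific to imaging. The end-of-treatment heading is slightly misaligned in the extracted text, but the row is empty in every column from week 40 to the 1-month visit, so the reading does not depend on it. The summary of changes records that end-of-treatment imaging was deleted to limit cost, which suggests that the blank is deliberate.

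**The gap.** On the 4-week month, the last scan before the landmark is 48 − 36 = 12 weeks early, which is 12/48 = 25% of the period. The next scan is at about 48 + 12 = week 60. The interval between scans is 60 − 36 = 24 weeks, against 12 weeks if the 3-monthly text were followed.

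**Inputs.** The plan gives no 12-month incidence, so I project from its 6-month design rates in Section 10.3: 40% (extensive stage) and 30% (limited stage) without effect, and half of these, 20% and 15%, at the targeted effect. As a check on these inputs, an exact two-sided binomial test with equal tails reproduces the plan's sample sizes. For 40% against 20%, the smallest n reaching 80% power is 45 (power 82.6%). For 30% against 15% it is 61 (power 80.4%).

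**Assumption.** The hazard is constant and there is no detection between scheduled scans. Neither is in the documents. With p the incidence at week 24,

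F(t) = 1 − (1 − p)^(t/24).

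For extensive stage without effect: F(36) = 1 − 0.6^1.5 = 53.5%; F(48) = 1 − 0.6^2 = 64.0%; F(60) = 1 − 0.6^2.5 = 72.1%. The share of 12-month events arising after week 36 is (F(48) − F(36))/F(48) = (64.0 − 53.5)/64.0 = 16.4%.

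| Group | p at week 24 | F(36) | F(48), target | F(60) | Share after week 36 |
|---|---|---|---|---|---|
| Extensive, no effect | 40% | 53.5% | 64.0% | 72.1% | 16.4% |
| Extensive, targeted effect | 20% | 28.4% | 36.0% | 42.8% | 21.0% |
| Limited, no effect | 30% | 41.4% | 51.0% | 59.0% | 18.8% |
| Limited, targeted effect | 15% | 21.6% | 27.8% | 33.4% | 22.0% |

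**Two ways to handle a late lesion.** If a lesion first seen at about week 60 is dated to that scan, it falls after the landmark and the estimate is F(36), which is too low. If the week-60 scan stands in for the missing one under Section 10.4, the estimate is F(60), which is too high. For extensive stage without effect, the reported figure could be 53.5% or 72.1% for a true 64.0%, a spread of 18.6 percentage points that comes only from which scan counts.

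**The case against.** The strongest reply is that the 12-month scan is in the plan. Sections 7.1 and 7.4 both call for 3-monthly head MRI, Section 7.5 allows MRI at end of treatment, and clinic visits and unscheduled imaging (Sections 7.4 and 7.7) would catch symptomatic cases. This stands in part. The plan does not simply lack a 12-month scan; its text and table contradict each other. If sites follow the text there is no gap, and if they follow the table, symptomatic detection makes the loss smaller than the table above shows. But an optional scan and a conflicting schedule do not secure a landmark assessment for every participant.

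A reader might infer three stronger things, none of which the documents support.

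- *That the 6-month primary endpoint is missed too, because six calendar months exceed 24 weeks.* Section 3.1 plans a head MRI at 6 months, the table places it at week 24, and Section 6.1 equates 4 weeks with a month. Any effect on the primary test would also depend on when the historical 40% and 30% were measured, which is not stated.
- *That the 12-month result must be biased in the device's favour.* Section 10.4 could equally let the follow-up scan stand in, which raises the incidence.
- *That the share at risk is 21% to 28%.* That range comes from the same model with month 12 at 52.2 calendar weeks, not at week 48 as the protocol's own convention has it.

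**Conclusion.** The point holds as an internal contradiction that affects one secondary endpoint. A site following Section 7.8 obtains no scheduled head MRI between week 36 and about week 60, so what would be reported as 12-month incidence is not measured at 12 months.

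The possible undercount is at most about 16% to 22% of 12-month events, given a constant hazard, month 12 at week 48 and no detection between scans. A hazard that falls over time, or symptomatic detection, would make it smaller. The direction of the bias is not fixed, because the plan does not say which scan counts. The primary endpoint and the sample sizes of 45 and 61 are unaffected.

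**What to change.** Reconcile Section 7.8 with Sections 7.1, 7.4 and 7.5 so that the promised 3-monthly head MRI is marked at week 48. In Section 3.2 or 10.2, state in weeks which scans count for the 12-month endpoint, and how a lesion first seen after that window is classified. The longest interval between scans around the landmark then falls from about 24 to about 12 weeks. The cost is one scan per participant still under assessment, which the text already promises.

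If the table is kept to limit cost, there are two options that need no extra scan:

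- Rename the secondary endpoint as 36-week incidence wherever it appears (synopsis, Sections 2.2, 3.2 and 10.2).
- Keep the 12-month endpoint and estimate it by an interval-censored method from the last clear and first positive scan. Week 48 lies inside the interval from week 36 to about week 60, so the estimate there rests on an assumed shape for the hazard. That shape should be specified in advance.

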4. STUDY ENROLLMENT AND WITHDRAWAL

4.1 PARTICIPANT INCLUSION CRITERIA

To be eligible to participate in this study, an individual must meet all of the following criteria:

1. Ability to understand and the willingness to sign a written informed consent document.
2. Age ≥ 22 years at time of informed consent. Both men and women and members of all races and ethnic groups will be included.
3. Pathologically confirmed LS-SCLC or ES-SCLC.
 - a. LSCLC – Stage I-III (T_{any}, N_{any}, M0) that can be safely treated with radiation doses. Excludes T3-4 due to multiple nodules that are too extensive or have tumor/nodal volume that is too large to be encompassed in a tolerable radiation plan.¹⁹
 - b. ESCLC – Stage IV (T_{any}, N_{any}, M1), or T3-4 due to multiple nodules that are too extensive or have tumor/nodal volume that is too large to be encompassed in a tolerable radiation plan.¹⁹
4. Must be no more than 6 weeks from having received last dose of chemo- and/or radiotherapy for primary tumor to anticipated start of TTField therapy.
5. Partial response to standard of care (chemo- and/or radiotherapy) as judged by treating physicians with no evidence of recurrence as observed by thoracoabdominal CT within 12 weeks of enrollment.
6. No brain metastases as observed by gd-MRI within 12 weeks of enrollment.
7. No previous or currently active second malignancy, with exception of non-metastatic prostate cancer, treated Stage I breast cancer, skin malignancies.
8. Life expectancy of at ≥ 3 months.
9. ECOG performance status ≤ 2 (Karnofsky ≥ 60 ; Refer to **Appendix A**).
10. Participants must be willing and able to fully comply with the minimum required 18 hours/day of TTField therapy.
11. Women of child-bearing potential must agree to use adequate contraception (hormonal or barrier method of birth control; abstinence) prior to study entry and for the duration of study participation.

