Secondary Objectives	1. Rate of brain metastases following TTField therapy at 12 months. 2. Overall survival of participants with SCLC after using TTField therapy. 3. TTField therapy related side-effects. 4. Quality of life among participants using TTField therapy. 5. Observed rate of brain metastases 6-month from the beginning of the 4 th cycle of chemotherapy to development of brain metastases
Primary Endpoints	Incidence of SCLC brain metastases at 6 months from the start of TTField therapy
Secondary Endpoints	1. Incidence of SCLC brain metastases at 12 months 2. Overall survival 3. Incidence of TTfield related adverse events 4. Quality of life 5. Incidence of SCLC brain metastases at 6 month from the beginning of the 4 th cycle of chemotherapy to development of brain metastases

	metastases
Number of Participants	A total of 106 participants will be enrolled in this study. Among these, target enrollment will include 45 participants with extensive stage disease, and 61 participants will have limited stage disease.
Duration of Therapy	Participants will receive TTField therapy for 12 months, or until development of brain metastases, whichever comes first.
Duration of Follow Up	Participant followed up will continue until death.
Inclusion Criteria	
 • ≥ 22 years of age • Biopsy-proven SCLC • Clinical Response to standard of care chemo- and/or radiotherapy, as defined by no thoracoabdominal tumor progression on CT imaging within 12 weeks prior to enrollment. • No contraindications to treatment with Optune®. • No other active malignancies, with exception of non-metastatic prostate cancer, treated Stage I breast cancer, skin malignancies • No brain metastases [gadolinium MRI < 12 weeks before enrollment]. • No mental conditions that would prevent compliance. • Life expectancy of at least 3 months. • ECOG ≤ 2.
Exclusion Criteria	
 • Progressive disease. • Pregnant • Implanted pacemaker, programmable shunts, defibrillator, deep brain stimulator, other implanted electronic devices in the brain, or documented clinically significant arrhythmias. • Evidence of increased intracranial pressure (midline shift > 5mm, clinically significant papilledema, vomiting and nausea or reduced level of consciousness)

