Participants with small cell lung cancer (SCLC) will be considered for enrollment if no more than 6 weeks have passed since last standard-of-care chemotherapy or thoracic radiation treatment of their primary tumor. Participants must have demonstrated partial response to treatment and show no tumor recurrence within 12 weeks prior to enrollment. Similarly, participants cannot have metastatic brain lesions in the 12 weeks leading up to enrollment. Participants eligible to receive Optune®-generated electrical tumor-treatment field (TTField) therapy will undergo continuous treatment for 12 months, or until disease progression, whichever comes first. This study will assess whether Optune® therapy to the brain can be used as a prophylactic approach to reducing the formation of brain lesions. The primary endpoint is the incidence of metastatic SCLC brain lesions. Participants will be clinically evaluated throughout the study for evidence of tumor recurrence or metastases, and will also be periodically assessed during the on-treatment and off-treatment portions of the study to evaluate treatment effects on quality of life and cognitive function. This study anticipates the accrual of 106 participants over 24-months.

TABLE OF CONTENTS

SUMMARY OF CHANGES.....	6
SYNOPSIS	7
SCHEMATIC OF STUDY DESIGN	9
LIST OF TABLES.....	16
LIST OF FIGURES	17
LIST OF ABBREVIATIONS.....	18
1. BACKGROUND INFORMATION AND SCIENTIFIC RATIONALE	20
1.1 Overview of Small Cell Lung Cancer (SCLC).....	20
1.1.1 Prophylactic Cranial Irradiation.....	20
1.2 Overview of Optune	20
1.2.1 Mechanism of action	20
1.2.2 Pre-clinical experience	20
1.2.3 Clinical studies of Optune.....	22
1.2.3.1 Effect of TTFields therapy on Recurrent GBM Subjects - A Pilot Study.....	22
1.2.3.2 Effect of TTFields therapy on Newly Diagnosed GBM Subjects - A Pilot Study	22
1.2.3.3 Pivotal Study for Recurrent GBM	23
1.2.3.4 TTFields therapy for newly diagnosed GBM.....	23
1.2.3.5 Effect of TTFields therapy for non-small cell lung cancer (NSCLC)	24
1.3 Rationale	24
1.4 Potential Risks and Benefits	25
1.4.1 Known Potential Risks.....	25
1.4.2 Known Potential Benefits	25
2. OBJECTIVES	26
2.1 Primary Objectives.....	26
2.2 Secondary Objectives	26
3. STUDY DESIGN AND ENDPOINTS	27
3.1 Description of the Study Design.....	27
3.2 Study Endpoints.....	27
3.2.1 Primary Endpoint.....	27
3.2.2 Secondary Endpoints	27

4. STUDY ENROLLMENT AND WITHDRAWAL	29
4.1 Participant Inclusion Criteria	29

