1.1 OVERVIEW OF SMALL CELL LUNG CANCER (SCLC)

Comprising approximately 14% of all lung cancers, SCLC has an annual incidence of 31,000 new cases, which are most often attributable to cigarette smoking. SCLC is characterized as having a rapid doubling time and early development of widespread metastases, and without treatment, the disease is associated with survival rates of 2 to 4 months.² SCLC is frequently classified as being either a limited-stage or extensive-stage.³ Limited disease (LS-SCLC) is defined as the patient having the SCLC involvement restricted to one hemithorax that can be encompassed within a tolerable radiation field. Alternatively, extensive disease (ES-SCLC) is defined as disease beyond one hemithorax and may include malignant pleural or pericardial effusion or hematogenous metastases.

The majority of patients (70%) present with ES-SCLC. Treatment with combination therapies is associated with a median survival time of approximately 9 to 10 months from diagnosis, and though 20% of these patients have a complete response, 5-year survival is only 2%.⁴ In contrast, LS-SCLC is associated with an 80% complete response rate and an approximate 18 months survival time. Multimodal treatment of LS-SCLC, which includes concurrent chemotherapy and radiotherapy, can achieve long-term disease-free of 20 to 25%.^{5,6}

PROPHYLACTIC CRANIAL IRRADIATION

Approximately 20% of patients with SCLC have a detectable brain lesion, and the actuarial risk of developing brain metastases within 2 years of diagnosis is nearly 80%.^{5,7,8} Randomized studies have shown that prophylactic cranial irradiation (PCI) decreases the risk of developing central nervous system metastases by more than 50%.⁷ The 3-year overall survival of complete responders (predominately those with LS-SCLC) that received PCI was 21%, whereas survival was only 15% in the control group.^{7,8}

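### No eligibility criterion addresses earlier brain metastases, so an extensive-stage patient whose lesions are no longer visible on MRI can enter this prevention trial and have a recurrence counted as a primary event.

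*Combined protocol and SAP*

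**What the plan says.** - Section 4.1, criterion 6: "No brain metastases as observed by gd-MRI within 12 weeks of enrollment".
- Synopsis, inclusion criteria: "No brain metastases [gadolinium MRI < 12 weeks before enrollment".
- Study overview under the design schematic: "participants cannot have metastatic brain lesions in the 12 weeks leading up to enrollment".
- Section 7.1, imaging subsection: "A gd-MRI of the head is required within 12 weeks prior to enrollment to assess presence of metastatic brain lesions".
- Section 4.1, criterion 3: limited stage is "LSCLC – Stage I-III (T_{any}, N_{any}, M0) that can be safely treated with radiation doses". Extensive stage begins "ESCLC – Stage IV (T_{any}, N_{any}, M1", with no metastatic site carved out.
- Section 4.2 lists eleven exclusions. None concerns earlier brain metastases or earlier brain irradiation. The last lets the investigator exclude a condition that would interfere with evaluating treatment or interpreting results.
- Section 1.3 states the aim: "We hypothesize that TTFields can be similarly adapted to prevent the formation of SCLC metastatic brain lesions".
- Sections 3.2 and 10.1: the primary endpoint is the incidence of SCLC brain metastases at 6 months from the start of TTFields, and everyone who starts TTFields is evaluable for efficacy. Neither section restricts the event to a first brain metastasis.

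**The concern.** Take a patient with brain metastases at diagnosis, treated with chemotherapy with or without brain irradiation, whose current MRI shows none. Read literally, sections 4.1 and 4.2 admit this patient. Such a patient is not at risk of a first brain metastasis. What the trial would observe is relapse of established disease, or control achieved by earlier irradiation.

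In a single-arm trial tested against a fixed 40%, eligibility is the main protection for the comparison, because no concurrent arm would carry the same mix. Patients prone to relapse would raise the observed rate and could hide a real effect. Patients already irradiated could lower it and suggest an effect that is not there. Section 10.2 does not name earlier brain metastases as a covariate, although it does allow tumor characteristics into the model building.

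**Working it through.** **1. The text.** In criterion 6, the Synopsis and section 7.1, the 12 weeks qualify the MRI. Only the overview states them as a period without lesions. Under either reading, history is not addressed. By contrast, criterion 7 covers both previous and current second malignancies.

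**2. Who is affected.** A lesion still visible on the qualifying MRI fails criterion 6. Limited stage requires M0, so brain metastases at staging would place a patient in the extensive-stage group. The gap is therefore extensive-stage patients whose lesions are no longer visible and who are within 6 weeks of their last chemo- and/or radiotherapy for the primary tumor (criterion 4).

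**3. The plan's own figure** (section 10.3: n = 45, null 40%, target 20%, two-sided exact test at 5%). Success for benefit needs the largest c with P(X ≤ c | 45, 0.40) ≤ 0.025:

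- P(X ≤ 11 | 45, 0.40) = 0.0216 and P(X ≤ 12 | 45, 0.40) = 0.0446, so c = 11.
- Power = P(X ≤ 11 | 45, 0.20) = 0.826.

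Forty-five is the smallest n that reaches 80% under this rule. The plan's figure reproduces.

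**4. Illustration.** Let f be the share of participants with earlier brain metastases and r their 6-month event rate. Both are assumed.

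- Power if the device works in everyone else: P(X ≤ 11 | 45, 0.20(1 − f) + r·f), with r from 0.40 to 0.60.
- False-claim probability if the device does nothing and these patients were irradiated: P(X ≤ 11 | 45, 0.40(1 − f) + r·f), with r from 0.20 down to 0.10.

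| f | Mixed rate, r = 0.40 to 0.60 | Power | Mixed rate, r = 0.20 to 0.10 | False-claim probability |
|---|---|---|---|---|
| 0 | 0.200 | 0.826 | 0.400 | 0.0216 |
| 2% | 0.204 to 0.208 | 0.8075 to 0.7881 | 0.396 to 0.394 | 0.0245 to 0.0261 |
| 5% | 0.210 to 0.220 | 0.7781 to 0.7250 | 0.390 to 0.385 | 0.0295 to 0.0343 |
| 10% | 0.220 to 0.240 | 0.7250 to 0.6074 | 0.380 to 0.370 | 0.0398 to 0.0529 |

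Fixing the number of affected patients, by adding two independent binomials, gives similar power: 2 of 45 gives 0.785 to 0.741, and 4 of 45 gives 0.739 to 0.639.

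**5. What an enrolled share requires.** Section 1.1 says "Approximately 20% of patients with SCLC have a detectable brain lesion" and that 70% present with extensive stage. Let q be the proportion of extensive-stage patients with brain lesions: 0.20, or 0.20/0.70 = 0.286 if all such lesions fall in extensive stage. Suppose a proportion x of them clear completely on MRI and enrol as readily as patients who never had lesions. Then f = qx/(qx + 1 − q), so x = f(1 − q)/(q(1 − f)).

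- f = 2%: x = 5% to 8%
- f = 5%: x = 13% to 21%
- f = 10%: x = 28% to 44%
- f = 20%: x = 62.5% to 100%

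The documents give no clearance rate. A 20% share would need most or all such patients to clear, so the table stops at 10%.

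**The case against.** The strongest case against is that this is silence in the wording, largely covered in practice. Participating sites send eligibility documents to the coordinating center for verification before enrolling (section 4.4.1.2). Exclusion 11 expressly reaches conditions that would interfere with interpreting results. Section 7.1 collects prior and current details of each participant's SCLC. These safeguards reduce the risk, and they make a corrected rule easy to apply. None of them states a rule on history, so a reviewer checking documents against criterion 6 would find nothing to reject.

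Four stronger readings are tempting, and the documents do not carry them:

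- *The rule is a 12-week look-back.* Only the overview says this. Elsewhere the 12 weeks are the permitted age of the scan, as in criterion 5 for CT.
- *Any patient with treated brain metastases is eligible.* A lesion still visible on the qualifying MRI is disqualifying.
- *The group is common because about 20% of SCLC patients have a detectable brain lesion.* That figure is not the share who clear on MRI and then enrol, as step 5 shows.
- *The 40% null is miscalibrated.* The documents do not describe the eligibility of the population behind it. The conflict with the prevention aim can be shown; a mismatch with the 40% cannot.

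The two scenarios also push in opposite directions, so no net bias is established.

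**Conclusion.** The concern holds as a gap in eligibility and endpoint wording. As written, the criteria admit extensive-stage patients with earlier brain metastases no longer visible on MRI, subject only to discretion. Their recurrences would count because the endpoint is not limited to first metastases and all treated participants are analysed. The plan does not say this outright; it follows from those two provisions.

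The size is uncertain and may be small. At an assumed 2% share, power is 79-81% against 82.6%; at 10% it is 61-73%. The false-claim probability stays between 2.5% and 5.3% across the assumed range. These figures rest on assumed shares and event rates. The sample sizes of 45 and 61 are not in error, and the limited-stage cohort is essentially unaffected. The change is worth making because it is cheap and makes the enrolled population match the stated aim.

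**What to change.** Reword criterion 6, with the matching Synopsis and overview lines, along these lines: *No known brain metastases, current or prior, at any time since the SCLC diagnosis, and none on the gd-MRI obtained in the 12 weeks before enrollment.* Check it against the available SCLC history and staging records at the central eligibility review that already takes place. The word *known* matters: the documents do not require brain imaging at diagnosis, so an earlier scan cannot be assumed for everyone.

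If anyone with earlier brain metastases is already enrolled, flag them and report the extensive-stage primary rate with and without them.

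The cost is a short amendment, one added eligibility item and slightly slower extensive-stage accrual. No new scan is needed, and the sample sizes stay at 45 and 61.
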